### **2.6.7 Discontinuation of the Study**

The whole study will be discontinued in any of the following cases:

- Sponsor decides to discontinue development of the compound or the study
- In the event of sponsor or regulatory authorities obtain safety information which does not allow continuation of the study

### **2.6.8 Management and Dosage Modifications for Unacceptable Hematologic and Non-hematologic Adverse Events**

National Cancer Institute Common Terminology Criteria for Adverse Events (NCI CTCAE) version 4.03 will be used to grade the severity of toxicities. An unacceptable toxicity is defined as the following treatment-related AEs:

- Grade 4 afebrile neutropenia >7 days despite optimal growth factor support
- Grade  $\geq 3$  febrile neutropenia or neutropenic infection
- Grade  $\geq 3$  thrombocytopenia with clinically significant bleeding or Grade  $\geq 3$  thrombocytopenia requiring a platelet transfusion
- Grade  $\geq 3$  nausea, vomiting, diarrhea, or electrolyte imbalances lasting greater than 48 hours despite optimal prophylactic and curative treatment
- Grade  $\geq 3$  allergic reaction
- Grade  $\geq 3$  other non-hematologic AEs
- Treatment delay >14 days secondary to recovery from study drugs- related AEs

**Table 1** summarizes the guidelines for dosage adjustment in the event of unacceptable AEs. Two dose reductions are allowed (from 40 mg to 30mg, or from 30 mg to 20 mg). If unacceptable AEs recur despite 2 dose reductions, the study treatment will be permanently discontinued and post-treatment follow-up ensues. However, if the patients are having clinical benefit, further treatment may be considered after discussion with the sponsor. In the event of AE, such as hematological AE-uncomplicated, necessitating 2 treatment interruptions, dose will be reduced when treatment resumes. However, if strongly needed for patient safety, dose can be reduced according to the investigator judgement, even if unacceptable hematological AE-uncomplicated is occurred once.

**Table 1: HBI-8000 Tablet Dosage Adjustment Guidelines**

AE Category	AE Description	Dosage interruption with/without Reduction
Hematological Adverse Events-- Uncomplicated	

• Neutropenia Grade 3 or 4 upon observation

• Thrombocytopenia Grade 3 or 4 upon observation

	Hold dose, initiate G-CSF, once resolved to $\leq 1$ within 2 weeks, resume at same dose.  Hold dose, once resolved to $\leq 1$ within 2 weeks, resume at same dose.  If recovery takes $>2$ weeks, discontinue study drug.
Hematological Adverse Events-- Complicated	

• Grade 4 afebrile neutropenia <math>> 7</math> days despite optimal growth factor support

• Grade <math>\geq 3</math> febrile neutropenia or neutropenic infection

• Grade <math>\geq 3</math> thrombocytopenia with clinically significant bleeding or Grade <math>\geq 3</math> thrombocytopenia requiring a platelet transfusion

	Hold doses, once resolved to $\leq 1$ within 2 weeks, resume at reduced dose (from 40 mg to 30 mg, or from 30 mg to 20 mg);  If recovery takes $> 2$ weeks, discontinue study drug.
Non-Hematological Adverse Events (excluding laboratory values without clinical significance)	Grade 3	Hold doses, once resolved to $\leq 1$ within 2 weeks, resume at reduced dose (from 40 mg to 30 mg, or from 30 mg to 20 mg), with appropriate prophylaxis as applicable.  If recovery takes $>2$ weeks, discontinue study drug.
	Grade 4	Discontinue study drug

The G-CSF is recommended to be prescribed when uncomplicated Grade 3 or 4 neutropenia is observed. Patient management should follow institution guidelines and be recorded in eCRFs. Laboratory tests should be obtained at least once a week to monitor recovery.

## **2.6.9 Management and Dosage Modifications for Non-Hematologic Adverse Events**

In the event of Grade 3 non-hematologic AEs (excluding isolated abnormality of laboratory values not associated with clinical significance), study medication should be held. Appropriate treatment should be initiated. Patients will be closely monitored for recovery and managed following the Dose Adjustment Guideline. If the AEs recur despite 2 dose reductions as applicable, study treatment should be discontinued. Study treatment should be terminated if Grade 4 non-hematologic adverse events occur, following the Dose Adjustment Guideline (Table 1).

## **2.7 Study Drug Administration**

During this the trial, patients will receive 40 mg of HBI-8000 administered approximately 30 minutes after any regular meal as four 10 mg tablets BIW continuously. The dosing interval would be 3 to 4 days for a total of 80 mg over 7 days. At each visit when study medication is dispensed, the study site staff will contact the Interactive Web Response System (IWRS) before dispensing.

## **2.8 Packaging, Labeling, and Storage**

HBI-8000 10 mg tablets are packaged in high density polyethylene bottles closed with an induction seal and a child-resistant cap and containing a desiccant pack, and a cotton coil. Each bottle contains 26 tablets. In case of discontinuation of treatment for any reason unused portion of the drug should be returned to hospital pharmacy.

Drug product will be stored at 2 to 8°C at hospital pharmacy until dispensing. After dispensing to patients, the drug will be transported to home in a cooler to maintain refrigerated condition. Once at home, the drug will be kept refrigerated until administration and out of reach of children all the time.

## **2.9 Patient Registration and Subject Number Assignment**

Based on medical history, potentially eligible patients will be identified. After obtaining informed consent, the screening procedures will be performed and a 5-digit subject number will be assigned. The first 3 digits are the site number (provided by the sponsor to study sites). The last 2 digits are a sequential number within a study site. If a patient is assigned a subject number and later found unable to begin HBI-8000 administration, the patient will be replaced. A new subject number will be assigned to the replacement patient.

## **2.10 Concomitant Treatments**

All concomitant medications, regardless of whether they are prohibited or not, received after signing informed consent must be recorded on the eCRF. Complete information on all concurrent medications (generic name of drugs, reason for use, dosage and duration of dosing, etc.) should be documented in the original records and in the eCRF.

Patients should consult their investigator prior to using medications other than the study drug, including over-the-counter medications and supplements.

### **2.10.1 Prohibited Medications and Therapy**

The following drugs are prohibited.

- Drugs known to produce significant QT prolongation and ventricular dysrhythmias (see [Appendix E](#))  
Prohibited from signing informed consent through the EoT assessment
- Anti-cancer therapy other than study medication

Prohibited during the study and within the following time intervals prior to the first dose of study drug.

- 4 weeks for anti-cancer chemotherapy
- 6 weeks for nitrosourea and mitomycin C
- 4 weeks for anti-cancer monoclonal antibody therapy

Corticosteroid prescribed for medical conditions other than lymphoma is not considered as an anti-cancer therapy for this study, for example: chronic obstructive pulmonary disease for allergy, topical steroids for rash.

-Please note that patient use of any prohibited medication is considered a protocol violation. In the event of prohibited medication use, investigator should consult study medical monitor to define an appropriate course of action if needed.

#### **2.10.2 Cautioned Medications**

Because the anti-emetic drug Zofran (ondansetron) is well known to prolong QTc, it is prohibited on 2 occasions, Cycle 1 Day 1 and Cycle 2 Day 1 when QTc test is scheduled. Starting 24 hours before the QTc test until the QTc test is completed on the next day, patient must not take Zofran over a 2-day period. Although anti-emetics are rarely needed for HBI-8000, if anti-emetics must be used for other medical reason, alternative drug(s) should be used. If a 5-HT3 antagonist must be used to manage severe emesis refractory to other medications, dosing should be postponed until resolution of underlying medical condition.

In case it is medically necessary to co-administer drugs that could interfere with CYP3A4 activity, investigators should monitor for toxicities and follow the study drug dose modifications for toxicity per study protocol. Also, St. John's wort should be used with caution.

#### **2.10.3 Permitted Medications**

Use of supportive care for AEs is permitted. These treatments may include anti-emetics, antipyretics, anti-diarrheal, anti-allergy agents, rash reliever, anti-hypertensive drugs, analgesics, antibiotics, hematopoietic growth factors, and transfusion with blood products.

Sulfamethoxazole Trimethoprim use is permitted. However, when its side effects are observed, alternative antibiotics prophylaxis should be considered.

#### **2.10.4 Dietary Restrictions**

Due to potential food-drug interactions for many commonly used medications, grapefruit, grapefruit juice, seville oranges, and any products that contain seville oranges or grapefruit should be avoided when possible.

## **2.11 Treatment Compliance**

The prescribed dosage, intervals between doses, and mode of administration (e.g., after meals, intact tablet [not crushed]) may not be changed without direction by the investigators. They must be recorded in the eCRFs.

The patient will be provided with a drug log to record dates and times of administration, time of meal prior to administration, AEs, and missed doses. To verify compliance, the patient will be instructed to bring the drug log and study drug bottles (including any empties) to appointments scheduled for Day 1 of each cycle starting with Cycle 2 for reconciliation.

At each visit when study medication is dispensed previously dispensed study drug count will be confirmed by the investigator, or authorized designee, and compliance assessed prior to dispensing new study medication.

Patients exhibiting poor compliance as assessed by tablet counts and not following dosing schedules should be counseled on the importance of good compliance to the study dosing regimen. Non-compliance to drug amount is defined as taking <75% or >125% of study medication during a cycle. Non-compliance to dosing interval is defined as more than 2 occurrences of <3 days between doses during a cycle, for example, 1 or 2 days between doses #3 and #4 instead of 3 or 4 days according to a BIW schedule. If in the opinion of the investigator, a patient is unable to follow instruction, study treatment should be discontinued.

## **2.12 Study Medication Accountability**

A clinical supplies shipment/receipt verification form will be enclosed with each study drug shipment. The site pharmacist who receives the shipment should complete this form and clinical research associate should collect a copy of the form at each pharmacy visit. If instead of the shipment/receipt verification form, a packing list is enclosed with the shipment, acknowledgment of the study drug receipt should be done through the IWRS system by the site pharmacist or authorized designee.

The investigator, or authorized designee, must maintain a complete and accurate record of the receipt and distribution of all study medication using the Drug Accountability Form. These forms will be described in detail in the pharmacy manual and must be available for inspection at any time.

All study medication supplies should be accounted for at the termination of the study, and a written explanation provided for any discrepancies. All unused study medication supplies and packaging materials are to be inventoried and returned to the local depot by the investigator, or authorized designee. The investigator, or authorized designee, is not permitted to return or destroy unused clinical drug supplies or packaging materials unless authorized by the sponsor or delegate(s).

## **3.0 STUDY ASSESSMENTS**

### **3.1 Efficacy**

#### **3.1.1 Primary Efficacy Endpoint**

The primary efficacy endpoint is the ORR, evaluated using the criteria of the International Consensus Meeting [Tsukasaki 2009] (modified) (see [Appendix D](#)).

Tumor response will be confirmed with central review by independent radiologist at end of study based on imaging studies prior to final efficacy analysis. The rates of PR, CR and PD will be assessed as applicable. Initial review will be performed by 1 independent radiologist. If the results differ from those reported by the investigators based on local radiology findings, a second independent radiologist will be asked to adjudicate by way of assigning the final disease response to the determination made by either the investigators or independent radiologist. The overall efficacy review will be done by independent oncologist for final efficacy analysis

#### **3.1.2 Secondary Efficacy Endpoints**

The secondary efficacy measures are:

- ORR by disease subtype (acute, lymphoma, and unfavorable chronic type)
- Median duration of PFS defined as the time from the first dose of study medication to objective tumor progression or death.
- Median DOR defined as the time from the first observation of tumor response to PD.

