## 2.6 Study Procedures Overview

Patients may be treated in this study as long as they receive clinical benefit (SD or a response) in the absence of unacceptable toxicity. Progressive disease would be determined by investigators based on local radiology findings and clinical judgement. No independent radiology review is required prior to designation of PD and treatment discontinuation. Independent Radiology Review and Independent Overall Efficacy Review will be performed for final efficacy analyses at the completion of this study.

To ensure patient safety, a data safety monitoring board (DSMB) will convene to review the cumulative safety profiles of study patients at following milestones: first 6 patients completing at least 1 cycle, 12, 18, 30 patients have been treated for at least 1 cycle; and at end of treatment (EoT) phase of the study. Based on the observed safety, dose and regimen of ongoing treatment may be modified as needed. For all patients, weekly safety laboratory tests will be obtained during the first 28 days and closely monitored for safety signals, especially the neutropenia and transaminase elevation.

It is estimated that each patient will be on study for up to 12 months after enrollment. Assuming that 24 months are needed to meet accrual target, the study period would be of 36 months to allow efficacy and safety determination. After study drug is discontinued, patients will be followed as described in [Sections 2.6.4](#) and [2.6.5](#).

Patients will be screened by the study site investigator prior to entry into the study. Patients will receive a detailed explanation of the study design, and the potential risk/benefit of treatment will be disclosed to patients prior to the screening process. Only eligible and consenting patients will be enrolled in the study. The investigator will maintain a screening log to record all patients screened.

Local radiology reports on disease status will guide investigator's decision on-study treatment, including discontinuation. At the end of the study, tumor response of each patient will be reviewed by independent radiologists and oncologists in a blinded fashion to obtain best response, dates of response and progression. The data from independent and local assessment will be analyzed in parallel in final study report.

The Schedule of Events is presented in [Table 4](#) of [Appendix A](#) (Section 9.1).

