#### **2.6.3 Treatment Phase**

All assessments must be performed as per the Schedule of Events (see [Appendix A](#)). Assessments scheduled on the day of study treatment should be performed prior to taking study drug, unless otherwise noted in the schedule of assessments.

Assessment of tumor response will be scheduled by end of the fourth week, eighth week, then every 8 weeks ( $\pm$  1 week) from C3D1. However, if a patient develops clinical signs and symptoms of PD, or unacceptable toxicity occurs, tumor assessment may be performed sooner as needed.

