#### **2.6.4 End of Treatment Safety Follow-up Visit**

All patients receiving at least 1 dose of HBI-8000 and discontinuing treatment for any reason except death will be evaluated approximately 30 ( $\pm$  3) days after the last dosing of study drug or before the initiation of new cancer treatment, whichever is earlier. Any patient for whom study treatment has been discontinued should complete study procedures listed in the EoT visit. At EoT safety visit, evaluations will include physical examination, vital signs, body weight, ECOG performance status, hematology, blood chemistry, urinalysis, pregnancy test (if applicable), ECG, and assessment of any ongoing AEs. If a patient discontinues study

treatment before PD is recorded, and if the last tumor assessment was >30 days earlier from the EoT visit, tumor assessment should be performed at EoT. In these patients, further tumor assessments are to be performed approximately every 3 months  $\pm$  2 weeks until PD or the start of new cancer therapy whichever occurs first, unless consent to study participation is withdrawn.

Patients with HBI-8000-related AEs of Grade  $\geq$  2 observed at the EoT visit should be followed-up and monitored monthly (phone calls/clinic visits) until the AEs have resolved to Grade  $\leq$  1 or are determined to be chronic, or patient receives other anti-cancer therapy.

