#### **2.6.5 Survival Follow-up**

Follow-up for survival (and tumor status in patients in whom PD has not yet been observed) should occur at approximately 3 month intervals after the EoT visit. Survival status may be conducted every 3 months  $\pm$  2 weeks by telephone contact or e-mail until death or end of study, defined as 12 months after the administration of the last dose of the entire study. The first subsequent anti-cancer therapy during this survival follow-up period should be recorded with regimen and start date in the appropriate Electronic Case Report Form (eCRF).

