## **5.0 STATISTICS**

### **5.1 General Statistical Considerations**

Protocol HBI-8000-210 is a Phase 2b Open-Label Single-Arm Study to Evaluate the Efficacy and Safety of Oral HBI-8000 in Patients with Relapsed or Refractory Adult T-Cell Lymphoma (ATL). The main analysis will be conducted for the purpose of regulatory submission of this product. The data cut-off (DCO) for the main analysis is set at the time when the last patient completes at least one post-efficacy assessment. The eCRF data by the DCO needs to be cleaned to have no unresolved queries. All independent reviews (including the independent radiological review, the Independent Overall Efficacy Review and review by the Data Safety Monitoring Board) by the DCO need to be completed before the main analysis. The data after the main analysis will be provided at the end of the study as a supportive material.

Statistical analysis for all safety, and efficacy parameters will be primarily descriptive in nature. Categorical variables will be summarized by frequency distributions (number and percentages of patients), continuous variables will be summarized by mean, standard deviation, median, minimum, maximum, and time-to-event variables will be summarized using Kaplan-Meier methods and figures for the estimated median time.

All analyses, summaries, and listings will be performed using Statistical Analysis System software (version 9.3 or higher)

A detailed methodology for summary and statistical analysis of the data collected in this trial will be documented in a statistical analysis plan (SAP) that will be dated and maintained by HUYA Biosciences. The SAP may modify the plans outlined in the protocol; however, any major modifications of the primary endpoint definition and/or its analysis will also be reflected in a protocol amendment.

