## **5.9 Efficacy Analysis**

The efficacy endpoints are the following:

Primary Endpoint:

- ORR; CR + CRu + PR

Secondary Endpoints:

- ORR by disease subtype (acute, lymphoma, and unfavorable chronic type)
- Median duration of PFS
- Median DOR

Exploratory Endpoint

- Median duration of OS

Response rate endpoints (ORR and ORR by disease subtype) will be summarized by number and percentage of patients meeting the definition of ORR along with the corresponding exact

95% CI. Tumor response as assessed by imaging studies will be adjudicated by independent radiology reviewers. Tumor lesions, such as skin lesion, that cannot be monitored by imaging studies will be determined by independent oncology reviewers and contributed to overall disease response assessment. Both investigators reported and independently adjudicated outcomes will be reported.

Primary analysis will be based on results from imaging studies and clinical data confirmed by Independent Central Review. Results from investigator assessment will also be reported.

Time-to event endpoints (PFS, DOR, and OS) will be summarized by Kaplan-Meier methods (median, 95% CI, number of events, number censored and Kaplan-Meier figures).

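### Duration of response ends only at progression, so a responder's death without recorded PD is not a DOR event, although the same section counts it for PFS

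*Combined protocol and SAP*

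**What the plan says.** The secondary endpoints in Section 3.1.2 define two time-to-event measures in adjacent bullets. The first is "Median duration of PFS defined as the time from the first dose of study medication to objective tumor progression or death". The second is "Median DOR defined as the time from the first observation of tumor response to PD". The synopsis, Section 2.3 and Section 5.9 only name DOR and add nothing to its definition.

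For the analysis, Section 5.9 states: "Time-to event endpoints (PFS, DOR, and OS) will be summarized by Kaplan-Meier methods". It promises the median, a 95% confidence interval and the numbers of events and censored patients. It does not say which outcomes are events or when a patient without an event is censored.

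Deaths are collected. Section 2.6.5 follows survival status "by telephone contact or e-mail until death or end of study".

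Section 5.1 leaves detailed methods to a separate SAP. None of its text on DOR is among the documents supplied.

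**The concern.** A response that ends in death has ended. If the definition stops only at PD, that death drops out of the event count for DOR while the same death counts for PFS. In a Kaplan-Meier analysis a patient without an event is normally censored. The curve then treats this patient as someone whose response might have continued, and it estimates response duration as if death without progression did not occur.

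DOR is a secondary, descriptive endpoint, so no test depends on it. It is still part of the main analysis, which Section 5.1 says is for regulatory submission. A reader would use it beside ORR to judge whether the responses last.

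**Working it through.** **1. Does PD already include death?** No.
- Appendix D (9.4.3.1 to 9.4.3.3 and Table 8) defines PD by lesion growth, skin findings, blood counts and new lesions.
- The independent reviews in 3.4.2 and 3.4.3 assign dates of response and progression only.
- The PFS definition lists progression and death as separate events, so the protocol itself distinguishes them.

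**2. What happens to a responder who dies without recorded PD?**

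| Endpoint | End event in 3.1.2 | Death without PD |
|---|---|---|
| PFS | progression or death | event |
| DOR | PD | not an event; handling not stated |

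**3. Is there a planned figure to reproduce?** No. The documents give no DOR median, event count or precision, and no rate of death without PD. Everything below is illustration on assumed inputs.

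**4. Large-sample size if the death is censored on its own date.** Let λ be the constant hazard of the first event after response, and f the share of first events that are deaths without PD (assumed 10, 20, 30%).
- Median with death counted: ln 2 / λ.
- Median with death censored: the PD hazard is (1 − f)λ, so the median is ln 2 / [(1 − f)λ].
- Ratio: 1 / (1 − f) = 1/0.9 = 1.11, 1/0.8 = 1.25, 1/0.7 = 1.43.

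For example, a PD-only median of 6 months corresponds to 5.4, 4.8 or 4.2 months when death counts (6 × 0.9, 6 × 0.8, 6 × 0.7).

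**5. Small-sample behavior.** Section 5.2 targets an ORR of 30% in 18 evaluable patients: 0.30 × 18 = 5.4, so about five responders. Suppose their responses end at 2, 4, 6, 8 and 10 months, with no other censoring. Take the median as the first time the Kaplan-Meier estimate S is at or below 0.5.
- All five are events: S = 0.8, 0.6, 0.4, so the median is 6.
- The one at 4 months is a death, censored: S = 0.8 at 2 months, 0.8 × 2/3 = 0.533 at 6, 0.533 × 1/2 = 0.267 at 8, so the median is 8.
- The one at 6 months is a death, censored: S = 0.8, 0.6, then 0.6 × 1/2 = 0.3 at 8, so the median is 8.
- A single death at 2, 8 or 10 months leaves the median at 6.

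One reclassified death can therefore move the median, but need not.

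**6. Direction.** Censoring a death on its own date removes a drop from the curve and leaves the numbers at risk unchanged, so the curve cannot be lower and the median cannot be earlier. Censoring at an earlier last assessment also removes the patient from the risk set sooner, and a fall is then possible. Take PD at 5, 6, 7 and 8 months and a fifth responder last assessed at 4 who dies at 7.5. The median is 7 with death counted and 7 if censored at death. If censored at 4 months, S is 0.75 at 5 months and exactly 0.5 at 6, so the median is 6. That fall depends on the S ≤ 0.5 rule; requiring S < 0.5 gives 7.

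**The case against.** Four points can be made on the other side.

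**The text never says the death is censored.** This stands. Censoring at death, censoring at the last assessment and treatment as a competing event are all open. What the document establishes is that the death is not a DOR event and that its handling is unstated.

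**The separate SAP may settle it.** It may, and a reader should not infer that the whole plan lacks censoring rules. That leaves the event definition in 3.1.2 as it is: a SAP that counted death would contradict it, and the two would need aligning.

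**Follow-up may record PD before most deaths.** A reader might infer that tumor status is lost once new therapy starts, because Section 2.6.4 continues assessments only "until PD or the start of new cancer therapy whichever occurs first". Section 2.6.5, however, also provides for following tumor status about every 3 months in patients without observed PD and names no stop at new therapy. Blood and skin are assessed on Day 1 of subsequent cycles (Appendix D, 9.4.1), and Section 2.6.3 allows earlier assessment on clinical signs of PD. The share f may therefore be small. It is not shown to be zero.

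**The numbers are assumptions.** This also stands. For five responders with no other censoring, the chance that the median becomes later or is not reached is 1 − (1 − f)² = 19, 36, 51% under the S ≤ 0.5 rule. Under S < 0.5 it is 1 − (1 − f)³ = 27, 49, 66%. The protocol states neither the rule nor f, so these percentages do not predict the trial's result.

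**Conclusion.** The DOR definition is wrong as written. It omits death, which PFS in the same section counts, and nothing in Appendix D supplies it. Under Kaplan-Meier with ordinary censoring this tends to overstate DOR and leaves the two endpoints inconsistent.

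The size is unknown, and it is zero if no responder dies without PD. The factor of about 1.1 to 1.4 rests on constant hazards, an assumed f of 10 to 30% and censoring at death. A reader might infer that the reported median must be too long. The documents do not support that: the median can stay the same, and under last-assessment censoring it can occasionally be earlier. ORR, sample size and alpha are untouched.

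**What to change.** In Section 3.1.2, define DOR as the time from first documented response to PD or death from any cause, whichever is first. Align the SAP with this definition and state its censoring rules consistently for DOR and PFS, including the censoring date for patients with neither event and the handling of new anti-cancer therapy before PD. Which convention to adopt for new therapy is the sponsor's choice; it needs to be written down.

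The cost is wording only. Section 2.6.5 already collects deaths, and the first subsequent therapy with its start date. The downside is a possibly shorter reported median DOR.
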